5.3 HUMAN DATA SHARING PLANS

5.3.1 Human Data Sharing Plan

Human data generated in this research will be shared for future research as follows:

- De-identified data in an NIH-funded or approved public repository
- Identified data in BTRIS

Data will be shared through:

- An NIH-funded or approved public repository: clinicaltrials.gov
- BTRIS
- Publication and/or public presentations.

Data will be shared at the time of publication or shortly thereafter.

5.4 RESPONSE CRITERIA

For the purposes of this study, patients in the operative arm will be re-evaluated for response every 3 months from M0 to M12, every 6 months from M12 to M24, and then every 12 months thereafter through M60. Patients in the non-operative arm will be re-evaluated for response every 3 months from M0 to M18, every 6 months from M18 to M30, and then every 12 months thereafter through M66.

5.4.1 Definitions

The following definitions will be used to determine if a given metabolic complication shows sufficient improvement in order to be considered as a component of a successful outcome.

5.4.1.1 Hypertension

Normalization and/or improvement in blood pressure as assessed by reduction in pharmacotherapy and/or normalization of blood pressure (systolic pressure ≤ 140 and diastolic pressure ≤ 90) from baseline.

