2.4 RANDOMIZATION (OR STRATIFICATION) PROCEDURES

Patients with subclinical hypercortisolism will be randomized to adrenalectomy or observation as defined above and followed for 6 months. At the end of 6 months, the patients who were in the observation-only arm will all be offered an adrenalectomy. Patients with subclinical hypercortisolism tend to have high prevalence of metabolic consequences, specifically hypertension, diabetes, osteoporosis, hypercholesterolemia, and/or obesity. The patients will be randomized by the CRO.

To be conservative, the primary goal of this study will be to determine if the use of adrenalectomy is associated with 35% improvement vs. 5% improvement over 6 months without surgery as defined for any one or more of the following associated metabolic complications: hypertension, diabetes, osteoporosis, hypercholesterolemia, and/or obesity. With 31 patients per arm (62 total), there would be 80% power to detect a difference of this magnitude using a 0.05 significance level two-tailed Fisher's exact test.

Abbreviated Title: Subclinical Hypercortisolism**Version Date: 12/19/2016**

The following definitions will be used to determine if a given metabolic complication shows sufficient improvement in order to be considered as a component of a successful outcome:

Hypertension: normalization and/or improvement in blood pressure as assessed by reduction in pharmacotherapy and/or normalization of blood pressure (systolic pressure ≤ 140 and diastolic pressure ≤ 90) from baseline.

Diabetes: normalization and/or improvement in diabetes as assessed by normalization (A1C $< 6.5\%$), and/or reduction and/or discontinuation of pharmacotherapy.

Osteoporosis: an increase in the level of bone formation markers greater than the least significant change, which is calculated by multiplying the “precision error” of the specific biomarker by 2.77 (95% confidence interval) as per the National Osteoporosis Foundation (NOF) Clinician’s Guide to Prevention and Treatment of Osteoporosis 2013 ([Appendix D](#)).

Hypercholesterolemia: improvement in cholesterol as assessed by a reduction or elimination of pharmacotherapy and/or reduction in LDL levels to the optimal risk stratified goal as defined by ATP III guidelines ([Appendix E](#)).

Obesity: improvement in obesity as defined by a ten percent reduction in fasting morning weight compared to baseline.

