5.4.1.2 Diabetes

Abbreviated Title: Subclinical Hypercortisolism

Version Date: 12/19/2016

Normalization and/or improvement in diabetes as assessed by normalization (A1C <6.5%), and/or reduction and/or discontinuation of pharmacotherapy.

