7 STATISTICAL CONSIDERATIONS

The primary objective of this study is to determine if the use of unilateral adrenalectomy is associated with normalization and/or improvement of hypertension, diabetes, osteoporosis, hypercholesterolemia, and/or obesity compared to medical treatment-only arm.

Patients with subclinical hypercortisolism will be randomized to adrenalectomy or medical treatment as defined above and followed for 6 months. At the end of 6 months, the patients who were in the medical treatment-only arm will all be offered an adrenalectomy. Patients with subclinical hypercortisolism tend to have high prevalence of metabolic consequences, specifically hypertension, diabetes, obesity and/or osteoporosis.

To be conservative, the primary goal of this study will be to determine if the use of adrenalectomy is associated with 35% who have improvement vs. 5% who improve over 6 months without surgery as defined for any one or more of the following associated complications: hypertension, diabetes, osteoporosis, hypercholesterolemia, and/or obesity. With 31 patients per arm (62 total), there would be 80% power to detect a difference of this magnitude using a 0.05 significance level two-tailed Fisher's exact test.

For the potential 31 patients initially randomized to observation and then undergoing an adrenalectomy at 6 months, the level of MAP, systolic, and diastolic pressure at 6 months but just before surgery will be compared to these values in the potential 31 patients initially randomized to immediate adrenalectomy 6 months after surgery using a Wilcoxon rank sum test. In addition, in the patients initially randomized to observation the changes in MAP from baseline to 6 months of observation as well as the declines in systolic and diastolic pressure from 6 months of observation until 6 months after surgery will be compared with a Wilcoxon signed rank test. Other important continuous parameters such as change in weight, triglycerides, total, HDL and LDL cholesterol, A1c, fasting glucose, and bone density may also be compared within patients using Wilcoxon signed rank test.

Abbreviated Title: Subclinical Hypercortisolism

Version Date: 12/19/2016

It is expected that 15-20 eligible patients may be able to enroll on this trial per year. In order to enroll 62 evaluable patients, it is anticipated that 3-4 years would be required. In order to allow for a small number of inevaluable patients, the accrual ceiling will be set at 66 patients.

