Biochemical markers of bone turnover. Suppression of biochemical markers of bone turnover after 3-6 months of specific antiresorptive osteoporosis therapies, and biochemical marker increases after 1-3 months of specific anabolic therapies, have been predictive of greater BMD responses and in some cases fracture risk reduction in large clinical trials. Biochemical marker changes in individuals must exceed the LSC in order to be clinically meaningful. The LSC is specific to the biomarker being utilized, which is calculated by multiplying the “precision error” of the specific biochemical marker (laboratory provided) by 2.77 (95% confidence level).

Biological variability can be reduced by obtaining samples in the early morning after an overnight fast. Serial measurements should be made at the same time of day. In order to have any clinical validity, sequential testing needs to be performed at the same laboratory.

Vertebral Imaging: Once the first vertebral imaging test has been performed to determine prevalent vertebral fractures (indications above), repeat testing should be performed to identify incident vertebral fractures if there is a change in the patient’s status suggestive of new vertebral fracture, including documented height loss, undiagnosed back pain, postural change, or a possible finding of new vertebral deformity on chest x-ray.

10.5 APPENDIX E - ATP III GUIDELINES**ATP III Guidelines (1)****Major Risk Factors (Exclusive of LDL Cholesterol) That Modify LDL Goals***

Cigarette smoking

Hypertension (BP \geq 140/90 mmHg or on antihypertensive medication)Low HDL cholesterol ($<$ 40 mg/dL)[†]Family history of premature CHD (CHD in male first degree relative $<$ 55 years; CHD in female first degree relative $<$ 65 years)Age (men \geq 45 years; women \geq 55 years)*

* In ATP III, diabetes is regarded as a CHD risk equivalent.

[†] HDL cholesterol \geq 60 mg/dL counts as a “negative” risk factor; its presence removes on risk factor from the total count.**LDL Cholesterol Goals and Cutpoints for Therapeutic Lifestyle Changes (TLC) and Drug Therapy in Different Risk Categories.**

Risk Category	LDL Goal	LDL Level at Which to Initiate Therapeutic Lifestyle Changes (TLC)	LDL Level at Which to Consider Drug Therapy
CHD or CHD Risk Equivalents (10-year risk $>$20%)	$<$ 100 mg/dL	\geq 100 mg/dL	\geq 130 mg/dL (100-129 mg/dL: drug optional)*

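### Blood pressure and A1C can score as primary successes by being at target, with no requirement that the patient was off target at baseline

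*Combined protocol and SAP*

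**What the plan says.** Section 2.4 sets the primary goal as "35% improvement vs. 5% improvement over 6 months without surgery as defined for any one or more" of five complications. Success on a single complication therefore decides the patient. Section 7 repeats the goal and sizes the trial on it: "With 31 patients per arm (62 total), there would be 80% power", with a two-tailed Fisher's exact test at the 0.05 level.

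The scoring rules stand in Section 2.4 and again in Section 5.4.1:

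- **Hypertension (5.4.1.1):** less drug treatment, or "normalization of blood pressure (systolic pressure ≤ 140 and diastolic pressure ≤ 90) from baseline".
- **Diabetes (5.4.1.2):** "Normalization and/or improvement in diabetes as assessed by normalization (A1C <6.5%), and/or reduction and/or discontinuation of pharmacotherapy".

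The Précis and Section 1.1.1 word the diabetes part differently. There, A1C has to improve to below 6.5%.

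On entry, exclusion 2.1.2.5 removes patients who have no metabolic complication. It gives no blood pressure or A1C threshold for having one.

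**The concern.** Each rule offers a route to success that is a level, and no section requires the patient to have been outside that level at the start. Take a treated diabetic with an A1C of 6.3% at entry and 6.3% at month 6, on unchanged drugs. Read literally, Section 5.4.1.2 scores this patient as a success in either arm. A treated hypertensive at 128/78 on both occasions raises the same question under Section 5.4.1.1.

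Such patients would be ordinary enrollees. The drug-reduction route makes sense only if patients are on treatment at entry, and Section 3.1 has both arms managed to national guidelines. Section 1.2 puts the prevalence of hypertension at 33 to 89% and of diabetes or impaired glucose metabolism at 15 to 66%.

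Two things are at stake. Patients who score whatever surgery does raise the success rate in both arms and shrink the difference between them. And two analysts could classify the same controlled patient in opposite ways on a binary primary endpoint with only 62 patients.

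**Working it through.** **1. The five rules side by side (Sections 2.4 and 5.4.1)**

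| Complication | Non-drug route to success | Change required? |
|---|---|---|
| Osteoporosis | Bone formation marker rises by more than the least significant change | Yes |
| Hypercholesterolemia | LDL reduced to its risk-based goal | Yes |
| Obesity | Weight down ten percent against baseline | Yes |
| Hypertension | At or below 140 and 90, with a reference to baseline | Implied; no baseline condition stated |
| Diabetes | A1C below 6.5% | None stated beyond the word normalization, which the parenthesis equates with a level |

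**2. The plan's own power.** Inputs from Section 7: 35% vs 5%, 31 per arm, two-sided 0.05, Fisher's exact test. Exact power is the sum, over all pairs (i, j), of Bin(i; 31, pT) × Bin(j; 31, pC), counting only pairs with a Fisher p-value of 0.05 or less. With pT = 0.35 and pC = 0.05 this gives 80.9%. The stated 80% is reproduced.

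**3. Allowing for patients at target at entry.** Let f be the share of patients in each arm who are already inside a success region at baseline and are scored as successes. Apply the planned rates to the rest:

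- pC = f + (1 − f) × 0.05
- pT = f + (1 − f) × 0.35
- difference = (1 − f) × 0.30

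For example, at f = 10%: pC = 0.10 + 0.90 × 0.05 = 0.145 and pT = 0.10 + 0.90 × 0.35 = 0.415.

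The documents do not give f, so a range is shown. The last column is the number per arm for 80% power from the continuity-corrected two-proportion formula. That formula is somewhat more demanding than the exact calculation, so its column should be compared with its own starting value of 34.

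| f (assumed) | Control | Surgery | Difference | Exact Fisher power, 31 per arm | N per arm for 80% |
|---|---|---|---|---|---|
| 0 | 5% | 35% | 30 points | 80.9% | 34 |
| 5% | 9.75% | 38.25% | 28.5 points | 68.7% | 41 |
| 10% | 14.5% | 41.5% | 27 points | 58.1% | 50 |
| 20% | 24% | 48% | 24 points | 40.9% | 70 |
| 30% | 33.5% | 54.5% | 21 points | 30.5% | 96 |

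A share of 10% is about three patients per arm (0.10 × 31 = 3.1) and costs 80.9 − 58.1 = 22.8 points of power. Most of the loss comes from the higher control rate, since the difference shrinks by only 3 points. The accrual ceiling in Section 7 is 66 in total, or 33 per arm.

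**The case against.** The text leans towards change. Section 5.4.1 introduces the definitions as a test of whether a complication has improved enough to count. The blood pressure rule refers to baseline, the objective has A1C improving to below 6.5%, and Sections 2.4 and 7 speak of improvement over six months. A planned control rate of 5% is itself hard to square with counting controlled patients as successes. So a reader who infers that the plan prescribes success on day 0 goes too far: on a plain reading, an unchanged controlled patient has not normalized. This stands. It does not close the gap, because the diabetes scoring rule drops the objective's wording, the blood pressure rule names no baseline condition, and no section says how a patient already at target is scored.

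A reader might also set the blood pressure cut-off against Appendix E, which lists hypertension as blood pressure at or above "140/90 mmHg or on antihypertensive medication", and conclude that the trial's definition of hypertension overlaps its definition of success. The documents do not support that. The entry belongs to a list of risk factors that modify LDL goals, attached for the cholesterol endpoint, and no section uses it for eligibility or for blood pressure response. There is no need to change the inequality signs.

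Two further points stand. The error would dilute the comparison rather than create a false positive. And the Wilcoxon comparisons of pressures between arms in Section 7 do not depend on the cut-offs, although they are not the primary test.

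**Conclusion.** The point holds as a gap in the primary-endpoint scoring rules. The A1C rule as written is a bare level and disagrees with the stated objective; the blood pressure rule is ambiguous. If patients at target on drugs at entry are scored as successes, the 5% control rate fails, and power drops from 80.9% to between 68.7% and 30.5% as f goes from 5% to 30%.

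These are scenarios, not an estimate of the trial's actual power. They assume a value of f that the documents do not supply, the same f in both arms, every such patient scored as a success, and the planned 35% and 5% applying unchanged to everyone else. The prevalence of hypertension in Section 1.2 does not give f, because it does not say how many patients are controlled at entry. If analysts apply the change reading throughout, f is zero and the stated design stands.

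**What to change.** In Sections 2.4, 5.4.1.1 and 5.4.1.2, and in matching words in the Précis and Section 1.1.1, add two statements:

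1. Normalization of blood pressure or A1C scores only if the pre-randomization baseline value (Section 2.5) was outside the protocol's own cut-off: systolic above 140 or diastolic above 90; A1C of 6.5% or higher.
2. A patient already within the cut-off at baseline can score on that complication only through the treatment-reduction route that the definition already contains. Scoring on the other complications is unaffected.

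The cut-offs themselves stay as they are. The change should be made in all five places, so that the objective and the scoring rules do not diverge again.

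The cost is small. Blood pressure (vital signs, 2.5.1) and A1C (2.5.7.10) are already collected before randomization, so no visit, test or patient is added. The downside is that controlled patients have fewer ways to score. The sponsor should therefore confirm that the 35% planned for surgery was meant on this change-based definition.

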5.4.1.2 Diabetes

Abbreviated Title: Subclinical Hypercortisolism

Version Date: 12/19/2016

Normalization and/or improvement in diabetes as assessed by normalization (A1C <6.5%), and/or reduction and/or discontinuation of pharmacotherapy.

5.4.1.3 Osteoporosis

An increase in the level of bone formation markers greater than the least significant change, which is calculated by multiplying the “precision error” of the specific biomarker by 2.77 (95% confidence interval) as per the National Osteoporosis Foundation (NOF) Clinician’s Guide to Prevention and Treatment of Osteoporosis 2013.

5.4.1.4 Hypercholesterolemia

Improvement in cholesterol as assessed by a reduction or elimination of pharmacotherapy and/or reduction in LDL levels to the optimal risk stratified goal as defined by ATP III guidelines.

5.4.1.5 Obesity

Improvement in obesity as defined by a ten percent reduction in weight compared to baseline.

5.5 TOXICITY CRITERIA

The following adverse event management guidelines are intended to ensure the safety of each patient while on the study. The descriptions and grading scales found in the revised NCI Common Terminology Criteria for Adverse Events (CTCAE) version 4.0 will be utilized for AE reporting. All appropriate treatment areas should have access to a copy of the CTCAE version 4.0. A copy of the CTCAE version 4.0 can be downloaded from the CTEP web site (http://ctep.cancer.gov/protocolDevelopment/electronic_applications/ctc.htm#ctc_40).

6 SAFETY REPORTING REQUIREMENTS/DATA AND SAFETY MONITORING PLAN

This is an observational protocol and thus no experimental treatments or procedures are performed as a part of this protocol and therefore no adverse events are expected. In the unlikely event that an adverse event occurs that is attributable to the research, CTCAE v. 4.0 will be used for grading such events. Patients who are undergoing standard of care work up and treatment of their disease may consent to have serum and urine collected and surgical and biopsy specimens, which are obtained during standard of care procedures, stored for ongoing and future research in the Endocrine Oncology Research lab. Patients who meet the standard of care criteria for resection of their disease will undergo a major operative procedure and may receive extensive care in the ICU. The principal investigator or designee will closely monitor and document the clinical care and treatment of each patient as per standard of care at the NIH Clinical Center. As per NIH Clinical Center standards of practice, the Occurrence Reporting System will be used to report any clinical events meeting these reporting criteria.

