- Thus, patients with subclinical hypercortisolism may benefit from operative intervention to halt or reverse metabolic complications associated with the disease and the risk of malignant progression.
- The optimal management of patients with subclinical hypercortisolism and adrenal incidentalomas is controversial and no large randomized trial has been conducted.
- We hypothesize that operative treatment would reduce the risk of long term complications of subclinical hypercortisolism and malignant progression, and propose a prospective randomized trial comparing nonoperative and operative management of subclinical hypercortisolism in patients with an adrenal neoplasm.

Objectives:**Primary Endpoints:**

- To determine whether unilateral adrenalectomy in patients diagnosed with subclinical hypercortisolism and adrenal neoplasm results in normalization and/or improvement of hypertension as assessed by reduction in pharmacotherapy and/or normalization of blood pressure (systolic pressure ≤ 140 and diastolic pressure ≤ 90), diabetes as assessed by reduction or elimination of pharmacotherapy and/or improvement in A₁C to $< 6.5\%$, osteoporosis by increase in bone formation markers indicative of increased bone formation, hypercholesterolemia as assessed by a reduction or elimination of pharmacotherapy and/or reduction in LDL levels to risk-stratified goal levels as defined by ATP III, and/or overweight or obesity as assessed by a 10 percent reduction in weight at 6 months.

Eligibility:

- An individual with an adrenal neoplasm less than 5 cm in size with biochemically confirmed evidence of hypercortisolism (2 out of 3: dexamethasone suppression test (DST) > 3 mcg/dL, elevated urine free cortisol, and/or morning ACTH < 2.2 pmol/l) without overt clinical signs and symptoms.
- Age greater than or equal to 18 years.
- Adults must be able to understand and sign the informed consent document.

Abbreviated Title: Subclinical Hypercortisolism

Version Date: 12/19/2016

- Patients must have laboratory and physical examination parameters within acceptable limits based on standard clinical practice.

Design:

- Prospective randomized study comparing adrenalectomy versus observation.
- Patients assigned to the operative arm will undergo adrenalectomy and then followed postoperatively for normalization and/or improvement of metabolic complications associated with hypercortisolism and histologic examination of the resected tumor.

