4.2 SAMPLE STORAGE, TRACKING AND DISPOSITION

Tissue will be snap frozen in liquid nitrogen and transported to the Endocrine Oncology Lab by calling [contact]. Samples will be labeled with the date and time of acquisition, the type of tissue and patient study ID. Upon receipt in the lab, samples will be bar coded and logged in to the tissue database, LabMatrix. Tissue will be stored in -20 °C or -80 °C freezers. All freezers are monitored and are on separate emergency generator lines.

Serum and urine samples for correlative studies may also be obtained and will be stored and tracked in the same manner as tissue samples.

At the completion of the protocol, the investigator will dispose of all specimens in accordance with the environmental protection laws, regulations and guidelines of the Federal Government and the State of Maryland. {Note, all patients undergoing surgery for endocrine diseases that consent to have their tissue used for research will be enrolled on this trial and thus the trial will remain ongoing as long as identified samples are being used in the conduct of this research. It is anticipated that this protocol will remain open for at least the next 6 years}

Any loss or unintentional destruction of the samples will be reported to the IRB.

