6.2.2 NCI-IRB Requirements for PI Reporting at Continuing Review

The protocol PI will report to the NCI-IRB:

1. A summary of all protocol deviations in a tabular format to include the date the deviation occurred, a brief description of the deviation and any corrective action.
2. A summary of any instances of non-compliance
3. A tabular summary of the following adverse events:
 - All Grade 2 **unexpected** events that are possibly, probably or definitely related to the research;
 - All Grade 3 and 4 events that are possibly, probably or definitely related to the research;
 - All Grade 5 events regardless of attribution;
 - All Serious Events regardless of attribution.

Abbreviated Title: Subclinical Hypercortisolism

Version Date: 12/19/2016

NOTE: Grade 1 events are not required to be reported.

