8.5 RISKS/BENEFITS ANALYSIS

The main risk of participation is related to the risk of complications in the adrenalectomy arm and worsening of the metabolic complications in patient in the observation arm. The risk of

Abbreviated Title: Subclinical Hypercortisolism

Version Date: 12/19/2016

adrenalectomy is less than 1% which would outweigh the potential benefit of reversal of metabolic complications. In patients in the observation arm, there may be worsening of the metabolic complications but all patients will cross over to the adrenalectomy arm after 6 months of follow up and will be medically treated as standard of care for the metabolic complications.

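### Section 6 calls this randomised surgical trial observational and Section 4.2 describes a different enrolled population, so attribution of non-serious harms from the assigned surgery or observation is left unclear

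*Combined protocol and SAP*

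**What the plan says.** The Précis describes the design as "Prospective randomized study comparing adrenalectomy versus observation". Sections 2.4, 3.1 and 7 agree: patients are randomised to adrenalectomy or to six months without it, after which the second group moves to surgery. Section 2.1 limits entry to adrenal neoplasms under 5 cm with biochemically confirmed hypercortisolism and excludes patients who have no metabolic complications. Section 7 caps accrual at 66.

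Section 6 says otherwise: "This is an observational protocol and thus no experimental treatments or procedures are performed as a part of this protocol". From that premise the section goes on to say that it foresees no adverse events. It ties the operation to usual care: "Patients who meet the standard of care criteria for resection of their disease will undergo a major operative procedure". The bracketed note in Section 4.2 says that "all patients undergoing surgery for endocrine diseases that consent to have their tissue used for research will be enrolled on this trial", and adds: "It is anticipated that this protocol will remain open for at least the next 6 years".

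Section 8.5 takes the opposite view of risk: "The main risk of participation is related to the risk of complications in the adrenalectomy arm". The same sentence adds worsening of metabolic complications in the observation arm. Section 8.4 puts the surgical complication risk below 1%.

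**The concern.** The Section 6 opening and the Section 4.2 note would suit a protocol that collects tissue from patients having surgery anyway. In this trial a random draw decides whether a patient is operated on now or waits six months. The protocol nowhere states that adrenalectomy, or assignment to observation, is the research intervention.

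That matters because two reporting rules turn on relatedness to the research. The continuing-review table in Section 6.2.2 asks for "All Grade 3 and 4 events that are possibly, probably or definitely related to the research" and applies the same test to unexpected Grade 2 events. The definition of an unanticipated problem in Section 6.1.8, which triggers the 7-day report in Section 6.2.1, requires at least a possible relation to participation. An investigator who follows Section 6 can call a complication of the assigned operation usual care. One who follows Section 8.5 would call it related. The trial weighs metabolic benefit against surgical risk, and Section 6.3.1 describes monitoring by the investigator and research team only, so what the IRB sees should not depend on which section was read.

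**Working it through.** **Step 1. Design and population, side by side.**

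| Topic | Sections 6 and 4.2 | Rest of the protocol |
|---|---|---|
| Type of study | Observational, nothing experimental (6) | Randomised, surgery or observation (Précis, 2.4, 3.1, 7) |
| Basis for surgery | Usual-care criteria for resection (6) | Random assignment, or crossover by 6 months (3.1) |
| Who is enrolled | All consenting endocrine-surgery patients (4.2) | Narrow adrenal group (2.1), at most 66 (7) |
| Research-only procedures | None (6) | PET/CT, DEXA and X-rays, with radiation for research only (8.5.1) |
| Expected harm | None (6) | Surgical risk below 1% (8.4); worsening under observation (8.5) |

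No row can be reconciled as it stands.

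**Step 2. Does the protocol's own risk figure support expecting no adverse events?** Section 8.4 gives only an upper bound of 1%. Assume independent patients with equal risk p and n operated patients. The expected count is n × p, and the chance of at least one complication is 1 − (1 − p)^n.

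- p = 1%, n = 62: 0.62 expected; 1 − 0.99^62 = 46%.
- p = 1%, n = 66: 0.66 expected; 1 − 0.99^66 = 48.5%.
- p = 0.5%, n = 62: 0.31 expected; 1 − 0.995^62 = 27%.

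Even with no complications in 62 patients, the one-sided 95% upper limit would be 1 − 0.05^(1/62) = 4.7%. These figures show scale only. They cover surgical complications, while Section 6.1.1 defines adverse events far more broadly.

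**Step 3. Which safety rules depend on attribution?**

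| Rule | Section | Depends on attribution? |
|---|---|---|
| Capture from enrolment to 30 days after surgery (Grade 1 events and non-supporting laboratory values in source documents only) | 5.2 | No |
| All serious events and all Grade 5 events at continuing review | 6.2.2 | No |
| Deaths within 7 days, except from progressive disease | 6.2.1 | No |
| Immediate report of safety concerns to the IRB | 6.3.1 | No |
| Grade 3-4 and unexpected Grade 2 events at continuing review | 6.2.2 | Yes, to the research |
| Unanticipated problem, and so its 7-day report | 6.1.8, 6.2.1 | Yes, to participation |
| Database capture more than 30 days after surgery | 5.2 | Yes, to the treatment; must also be serious and unexpected |
| Serious events more than 30 days after the last study procedure | 6.1.1 | Yes, at least possibly, to the agent or intervention |

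**Step 4. The same event under each premise.**

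- Non-serious Grade 3 complication within 30 days of surgery: in the database either way. It is in the IRB table under Section 8.5 and can be left out under Section 6.
- Non-serious Grade 3 metabolic worsening during observation: recorded either way, because Section 6.1.1 counts worsening of an existing condition and no surgery has yet started the 30-day clock. The IRB table is again uncertain.
- Serious complication: in the IRB table either way.
- Death not from progressive disease: reported within 7 days either way.

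**Step 5. Late events.** Section 5.2 captures a late event only if it is serious, unexpected and treatment-related. Section 6.1.1 asks only for a possible relation and counts its 30 days from a different point. Section 6.2.2 tabulates all serious events with no attribution test. These three do not agree.

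**Step 6. Power.** Section 7's 80% reproduces: exact enumeration of the two-sided Fisher test with 31 per arm, 35% against 5%, gives 80.9%. Nothing in this point changes it.

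**The case against.** A reader might infer that harms of the assigned adrenalectomy go unreported. The documents do not support that. The four rules in Step 3 without an attribution test cover the perioperative period, every serious event, and every death other than from progressive disease. Seriousness in Section 6.1.4 includes hospitalisation or its prolongation and important medical events, so many Grade 3-4 surgical complications would reach the IRB by that route. Nor would the trial's own count of perioperative harms be short, because the Section 6.2.2 filter governs a summary table and not database capture.

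The unrelated judgement is also hypothetical. Nothing in Sections 6.1.8 or 6.2 says that surgery is outside the research, the threshold is only a possible relation, and Section 8.5 supports counting both surgical and observation-arm harms as risks of participation. An unanticipated problem must in addition be unexpected and suggest greater risk than was known, so recognised complications at the expected rate would not qualify on any reading.

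Section 3.4 has the operation done to the standard of care, which may be all that Section 6 meant. But that describes how the surgery is performed, not why this patient receives it now.

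A reader might also infer from Section 4.2 that the trial is open to all endocrine-surgery patients. Enrolment runs through Section 2.1 and the eligibility checklist in Section 2.3, and Section 4.1 sends biospecimen collection to a separate protocol, so the note has no shown effect on who is randomised.

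All of this stands and narrows the consequence. The contradiction remains, and so does the absence of any statement on attribution.

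**Conclusion.** Section 6 and the Section 4.2 note are wrong as written for this trial. The consequence is a limited reporting gap: non-serious Grade 3-4 and unexpected Grade 2 events can drop out of the continuing-review table, and a non-fatal unanticipated problem can miss its 7-day report. This rests on the assumption that an investigator relies on Section 6 when judging relatedness; the documents permit that reading but do not require it. The late-event rules use treatment or intervention as the reference, so they may still cover adrenalectomy.

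Up to 66 patients are exposed if all are operated on (33 by initial assignment if arms are equal, 66 − 33 = 33 by crossover). How many reportable events that means cannot be derived from the documents.

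This should be fixed. It does not touch the primary endpoint, power or analysis.

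**What to change.** 1. In Section 6, remove the statements that the protocol is observational, performs nothing experimental and expects no adverse events.
2. Remove the bracketed enrolment note from Section 4.2.
3. Reconcile the Section 6 sentence on usual-care resection with Sections 2.1 and 3.1. Who is operated on is for the trial team to settle; the passages only need to agree.
4. Add a statement that, for Sections 6.1.8, 6.2.1 and 6.2.2, events at least possibly attributable to the assigned adrenalectomy (initial or at crossover) or to the assigned observation period count as related to the research.
5. Reconcile the late-event rules in Sections 5.2 and 6.1.1 with each other and with the serious-event line of Section 6.2.2.

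The cost is a wording amendment, a few more events in the IRB table, and a stated safety profile that may look slightly less favourable.
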